7.3 Statistical Analysis

Details of all statistical analyses will be described in the SAP.

All data collected will be presented in data listings. Data from participants excluded from an analysis set will be presented in the data listings but not included in the calculation of summary statistics for that analysis set.

For categorical variables, frequencies and percentages will be presented. Continuous variables will be summarised using descriptive statistics (number of participants, mean, median, minimum, and maximum).

Baseline demographic and background variables will be summarised by study vaccine group. The number of participants who enrol in the study and the number and percentage of participants who complete the study will be presented. Frequency and percentage of participants who withdraw or discontinue from the study, and the reason for withdrawal or discontinuation, will also be summarised.

7.3.1 Efficacy Analyses

The primary endpoint will be analysed on the PP-EFF Analysis Set and supported by analysis of the ITT Analysis Set. Conclusions concerning declaration of attainment of the primary endpoint at the completion of the study will only be based on the PP-EFF population.

VE is defined as VE $(\%) = (1 - RR) \times 100$, where RR = relative risk of incidence rates between the 2 study vaccine groups (SARS-CoV-2 rS with Matrix-M1 adjuvant or placebo). The final analysis for the primary objective in the PP-EFF population will be carried out at the overall one-sided Type I error rate of 0.025 for the 3 planned analyses. The nominal alpha to be spent for the final analysis will be recalculated using the Lan-DeMets alpha spending function based on the actual numbers of events used for the interim analyses and the numbers of endpoints to be used for the final analysis. The estimated RR and its CI will be derived using Poisson regression with robust error variance [Zou 2004]. The explanatory variables in the model will include study vaccine group. The dependent variable will be the incidence rate of the endpoint of interest. The robust error variances will be estimated using the repeated statement and the participant identifier. The Poisson distribution will be used with a logarithm link function. The site (depending on the distribution of endpoints) and the age strata will be included in the model as covariates. To assess incidence rates rather than absolute counts of cases, accounting for differences in follow-up times starting with 7 days after the second vaccination among participants, an offset will be utilized in the Poisson regression. In case the total number of events to be analysed may be too low for an asymptotic method proposed (i.e., ≤ 5 events in either treatment group), an alternative method based on the single sample exact binomial distribution may be used for the analysis. This method is based on the proportion of the events in the SARS-CoV-2 rS with Matrix-M1 adjuvant group among the total number of events observed in both treatment groups after

SARS-CoV-2 rS Vaccine Novavax, Inc.

adjusting for the differential number of subjects (or inclusive of differential lengths of follow-up) between the 2 treatment groups.

Hypothesis testing of the primary efficacy endpoint will be carried out against H0: VE \leq 30%. Rejection of the null hypothesis, H0: VE \leq 30% demonstrates a statistically significant vaccine effect (i.e., alpha-adjusted lower bound confidence interval [LBCI] > 30%) will be considered meeting the prespecified study success criterion. The study will also continue for the intended duration to measure efficacy, immunogenicity, and safety endpoints, regardless of primary endpoint success at the interim analyses or the final efficacy analysis. The final formal analysis of the primary efficacy endpoint will be triggered when approximately 152 PP-EFF participants with symptomatic mild, moderate, or severe COVID-19 endpoints have accrued. Also, in order to be able to respond to the unexpected and rapidly evolving COVID-19 pandemic situation globally, other factors such as requests by government or public health agencies may also be factored into the decision-making to unblind the study for the final analysis, but this always occurs in consultation with lead regulatory agencies.

The secondary and exploratory efficacy endpoints will be analysed using the same method as the primary efficacy analysis described above. Analysis of secondary and exploratory efficacy endpoints will be performed without adjustment for multiple comparisons (i.e., two-sided alpha of 0.05). The final interpretation of the overall vaccine efficacy will be based on the totality of statistical evidence, including immunogenicity results and the clinical importance in discussions with the regulatory agencies and scientific communities. The EOS analysis will be performed when the last participant completes the last visit (12 months after the last study vaccination) or discontinues earlier.

7.3.2 Immunogenicity Analysis and Correlates of Risk

The primary and secondary immunogenicity analyses will be performed using the PP-IMM and ITT analysis populations.

For the serum antibody levels measured by microneutralization and HAI assays, the geometric mean at each study visit, the geometric mean fold rises (GMFRs) comparing to Day 0 (baseline) at each follow-up study visit, along with 95% CI will be summarised by study vaccine group. The 95% CI will be calculated based on the t distribution of the log-transformed values for geometric means or GMFRs, then back transformed to the original scale for presentation. The seroconversion rate (SCR), proportion of participants with \geq 4 fold rises if naïve at baseline, along with 95% CIs based on the Clopper-Pearson method will be summarised by study vaccine group at each follow-up study visit.

For the subset of participants who receives the influenza vaccine concurrently with the study vaccines, comparisons of strain-specific immune responses to influenza vaccine as measured by HAI will be performed. The treatment comparison will be made by comparing the strain-specific GMTs and the SCRs. The SCR is defined as the proportion of subjects with either a

baseline reciprocal (Day 0) titre of < 10 and a post-vaccination reciprocal titre \ge 40, or a baseline titre of \ge 10 and a post-vaccination titre \ge 4-fold higher.

For strain-specific GMTs in each treatment group, titres reported below the lower limit of quantitation (LLOQ; i.e., below the starting dilution of assay reported as "< 10") will be set to half that limit (i.e., 10 / 2 = 5). Strain-specific GMTs will be summarized by treatment group and visit day along with the corresponding two-sided 95% CIs, by exponentiating the corresponding log-transformed means and their 95% CIs. The ratio of GMTs between treatment groups post-vaccination and the corresponding two-sided 95% CI will be calculated on log-transformed titres using the analysis of covariance (ANCOVA) with treatment group and baseline (Day 0) measurement as the covariate.

For strain-specific SCRs, the rate in percent and the corresponding two-sided exact binomial 95% CIs will be calculated using the Clopper-Pearson method. The two-sided 95% CIs for the absolute rate difference between the 2 treatment groups will be constructed using the Newcombe method.

Similar summaries will be generated for the other immunogenicity endpoints and other assays if conducted.

Correlates of risk will be assessed where immune responses are measured in all available participants, and the results compared between participants who experience a SARS-CoV-2 event and participants who do not. The goal of this analysis is to assess correlates of risk of SARS-CoV-2 infection (and potential other secondary endpoints) in the study vaccine group by comparing study vaccine-induced immune responses associated with COVID-19.

The EOS analysis will be performed when all participants in the Neutralisation Assay Subset have completed the last study visit or discontinued earlier.

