3.1 Study Vaccination Pause Rules

Study vaccination pause rules based on reactogenicity, AEs, and SAEs related to study participation will be in place to monitor participant safety during the study.

AEs meeting any one of the following criteria will result in a hold being placed on subsequent study vaccinations pending further review by the SMC at the direction of the SMC chair:

• Any toxicity grade 3 or higher (severe or potentially life-threatening) solicited (local or systemic) single AE term occurring in ≥ 10% of participants (after a minimum of 100 subjects are enroled) in the SARS-CoV-2 rS with Matrix-M1 adjuvant group within the first 7 days after study vaccination.

• Any severe unsolicited single AE preferred term for which the investigator assesses as related that occurs in ≥ 5% of participants (after a minimum of 100 subjects are enroled) in the SARS-CoV-2 rS with Matrix-M1 adjuvant group, within the first 7 days after study vaccination.

In addition, any SAE assessed as related to vaccine (final assessment by the sponsor) will be reported by the sponsor to the SMC Chair as soon as possible, and within 24 hours of the sponsor's awareness of the event. Based on this initial report of the event to the SMC Chair, the Chair may advise the sponsor to immediately pause enrolment and further dosing in either some or all subjects in the study and to convene an ad hoc meeting, or make alternative recommendations. The SMC Charter defines processes for how this review will occur and how the Chair's recommendations will be documented.

The sponsor, along with medical monitor, may request an SMC review for any safety concerns that may arise in the study, even if they are not associated with any specific pause rule; for example, any SAE for which causality is at least possibly related.

The 400 subject influenza vaccine co-administration study will utilize the same pause rules with one difference due to the expectation of greater reactogenicity and the small size:

Any grade 3 or higher (severe or potentially life-threatening) solicited (local or systemic) single AE term occurring in ≥ 20% of participants in the SARS-CoV-2 rS with Matrix-M1 adjuvant plus seasonal influenza vaccine group, within the first 7 days after study vaccination.

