5. TEST ARTICLES

5.1 Study Vaccines Administered

Study vaccinations (SARS-CoV-2 rS with Matrix-M1 adjuvant or placebo) will comprise 2 IM injections (Day 0 and Day 21), ideally in alternating deltoids. For blinding purposes, all participants will be vaccinated using the same injection volume (i.e., 0.5 mL). The dose level will be 5 µg SARS-CoV-2 rS with 50 µg Matrix-M1 adjuvant (co-formulated in a single vial); placebo will be saline for injection. Study vaccinations will be administered on an outpatient basis by designated site personnel in a way to maintain the blind. Any pharmacy preparation with unblinded product will require unblinded site personnel who will not otherwise be involved in the study procedures or observation of participants.

The seasonal influenza vaccine co-administration sub-study will comprise a single IM injection (0.5 mL) of a licensed influenza vaccine on Day 0, ideally in the opposite deltoid of the study vaccine. Seasonal influenza vaccine will be administered in an open-label manner. Flucelvax Quadrivalent will be given to those 18 to 64 years of age, and an adjuvanted trivalent influenza vaccine will be given to those ≥ 65 years of age.

Whenever possible the RIGHT deltoid will be used for the influenza vaccine and the LEFT deltoid for the study vaccine.

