5.3 Method of Assigning Participants to Study Vaccine Groups

Participants will be randomly assigned in a blinded manner using the centralised Interactive Response Technology (IRT) according to pre-generated randomisation schedules. Participants will be randomised in a 1:1 ratio via block randomisation to receive 2 IM injections of the SARS-CoV-2 rS with Matrix-M1 adjuvant or placebo. Randomisation will be stratified by site and by age ≥ 65 years. The first approximately 400 participants who qualify for the seasonal influenza vaccine co-administration sub-study (which may be at select study locations only) will be assigned prior to randomisation. These participants will be part of the solicited AE safety subset analysis. Details regarding the IRT process will be provided separately to the sites.

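### The HAI analysis ignores that age decides the influenza vaccine, so for the one strain absent from the trivalent product any interference is diluted toward no effect

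*Protocol*

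**What the plan says.** Protocol Section 5.1 ties the influenza product to age: "Flucelvax Quadrivalent will be given to those 18 to 64 years of age", while "an adjuvanted trivalent influenza vaccine will be given to those" aged 65 and over. Section 3 gives the purpose of the HAI assay, which is to see whether the study vaccine affects the response to the influenza vaccine.

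Section 7.3.2 sets out the analysis in some detail, and the Synopsis repeats it. The GMT ratio is "calculated on log-transformed titres using the analysis of covariance (ANCOVA) with treatment group and baseline (Day 0) measurement as the covariate". For the summaries, "Strain-specific GMTs will be summarized by treatment group and visit day along with the corresponding two-sided 95% CIs". For seroconversion, "The two-sided 95% CIs for the absolute rate difference between the 2 treatment groups will be constructed using the Newcombe method". None of these steps separates the two products, limits a strain to those who received it, or includes age.

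Age at 65 is nevertheless a randomisation stratum (Section 5.3), and the age strata enter the efficacy model (Section 7.3.1).

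On reactogenicity, Section 5.3 says of the sub-study: "These participants will be part of the solicited AE safety subset analysis". Section 3.1 gives the sub-study a different pause threshold "due to the expectation of greater reactogenicity and the small size".

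**The concern.** A quadrivalent vaccine carries one strain more than a trivalent one. For that strain, participants aged 65 and over have no vaccine response with which the study vaccine could interfere. Their GMT ratio between arms should be about 1 and their seroconversion about nil in both arms. Including them averages a real contrast with a null one, so the estimate moves in one direction only, toward no interference. Detecting interference is the reason for the HAI comparison.

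The model is written into the protocol rather than left open, so an analysis plan that followed it would carry the problem forward.

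A secondary issue concerns solicited events. Systemic symptoms may not be assigned to either injection (Section 6.4.1.1.2), and the protocol itself expects more reactogenicity with co-administration. First-dose systemic rates that blend the sub-study with the Safety Subset describe neither regimen cleanly.

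**Working it through.** The protocol gives no power, margin, standard deviation or sample-size derivation for the HAI comparison, so there is no stated figure to reproduce.

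**Inputs from the protocol.** About 400 participants, allocated 1:1; randomisation stratified at age 65; product fixed by the same cut; ANCOVA on treatment group and baseline titre.

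**Assumptions.**
- The trivalent strains are among the four quadrivalent strains.
- Trivalent recipients do not respond to the fourth strain.
- The share aged 65 and over, *f*, is the same in both arms. Its value in the sub-study is not given. The whole-trial target is at least 25% (Section 3), so 20% to 40% is used here.

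**Missing strain, GMT ratio.** Let R be the true ratio in quadrivalent recipients. The log ratio is R's with weight (1 − f) and zero with weight f:

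pooled ratio = exp[(1 − f) × ln R] = R^(1 − f)

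For R = 0.67, ln R = −0.400:

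| f | (1 − f) × ln R | Ratio that appears |
|---|---|---|
| 20% | −0.320 | 0.73 |
| 25% | −0.300 | 0.74 |
| 30% | −0.280 | 0.76 |
| 40% | −0.240 | 0.79 |

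**Missing strain, seroconversion.** Pooled difference = (1 − f) × the difference at 18 to 64. A 15-point loss appears as 0.80 × 15 = 12.0 points at 20%, 11.3 at 25% and 0.60 × 15 = 9.0 at 40%.

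**Check by simulation.** 400 participants, 1:1, f = 25%, 3,000 replicates; assumed residual SD 0.35 log10, with a rise of 0.6 log10 to the fourth strain in quadrivalent recipients and none in trivalent recipients.

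| Analysis of the missing strain | Estimate when truth is 0.67 | SE (log10) | Estimate when truth is 0.80 | 95% CI wholly below 1 when truth is 0.80 |
|---|---|---|---|---|
| As the protocol states | 0.74 | 0.042 | 0.85 | 37% |
| Age stratum added as covariate | 0.74 | 0.035 | 0.85 | 54% |
| Quadrivalent recipients only | 0.67 | 0.040 | 0.80 | 67% |

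The covariate narrows the interval around the same diluted value. Only restriction recovers the true ratio. Although restriction drops a quarter of the participants, its standard error is no larger than that of the stated model, because the gap between immunised and unimmunised people leaves the residual.

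**Shared strains.** With a true ratio of 0.67 in both age groups and a smaller assumed rise (0.4 log10) in the older group, the stated model returns 0.67. Its SE is 0.036, against 0.035 with age in the model, a difference of about 3%.

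**Solicited events.** If the two groups do not overlap, the sub-study is 400 / (2,000 + 400) = 17% of those with solicited data.

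**The case against.** The strongest reply concerns scope. HAI comparisons are made strain by strain, so dilution cannot spread from the missing strain to the others. A reader might infer that pooling ages masks interference in general. The documents do not support that: randomisation is stratified by age, the shared-strain ratio is unbiased when interference is equal across ages, and the precision loss is slight.

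A reader might also infer that interference on the missing strain would go unseen. That is too strong for a large effect. At 25% aged 65 and over, 0.74 with SE 0.042 log10 gives a 95% interval of about 0.61 to 0.89, which still excludes 1. Loss of detection matters for a moderate effect such as 0.80.

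It is fair to say that the objective is exploratory (Section 2.1.3), that no margin or decision rule depends on it, and that Section 7.3 refers details to the statistical analysis plan, which may define who is evaluable for each strain. The first two points limit the stakes. The third does not dispose of the matter, because the protocol names the model terms and leaves product and age out.

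On solicited events, a reader might infer that the vaccine-versus-placebo comparison is confounded. It is not: both arms of the sub-study receive influenza vaccine. That vaccine is given on Day 0 only, local reactions are recorded for the study-vaccine site only, and Section 7.3.3 names the two groups separately. What remains is a descriptive question about systemic events after the first dose. The 17% is a headcount and does not measure bias.

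**Conclusion.** The point holds for one strain. As specified, the GMT ratio and seroconversion difference for the strain absent from the trivalent vaccine are biased toward no interference. A true ratio of 0.67 appears as 0.73 to 0.79 if 20% to 40% of the sub-study is aged 65 or over, and 0.74 at 25%. This rests on the assumed age share and on trivalent recipients having no response to that strain; any cross-reaction would lessen the dilution. The simulated detection rates rest further on an assumed standard deviation and rise.

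For the shared strains the matter is one of modest precision and clear presentation, with no bias unless interference differs by age or product. The harm is to one exploratory estimate and its interval, not to a formal test. It is worth correcting because the direction of error runs against the purpose of the comparison. The reactogenicity point is secondary.

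**What to change.** In Section 7.3.2 and the Synopsis, and carried into the analysis plan:

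- **Missing strain:** estimate the GMT ratio and seroconversion difference in quadrivalent recipients (18 to 64) only. Do not rely on an age covariate for this strain.
- **Shared strains:** add the age stratum, which is also the vaccine product, to the ANCOVA, and present GMTs and seroconversion by stratum.
- **Secondary:** also tabulate first-dose solicited systemic events separately for the co-administration sub-study and the Safety Subset of about 2,000.

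The cost is a few lines of wording, a few extra tables and fewer participants for one strain. No data collection changes.

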7.3.3 Safety Analyses

Solicited AEs (e.g., local and general systemic reactogenicity symptoms) will be captured in the Safety Subset of approximately 2,000 participants and in the seasonal influenza vaccine co-administration sub-study of approximately 400 participants.

Numbers and percentages (with 95% CIs based on the Clopper-Pearson method) of participants with solicited local and systemic AEs through 7 days after each study vaccination will be summarised by study vaccine group and the maximum toxicity grade over 7 days after each study vaccination. The duration of solicited local and systemic AEs after each study vaccination will also be summarised by treatment group.

Unsolicited AEs will be coded by preferred term and system organ class using the latest version of the MedDRA and summarised by study vaccine group as well as by severity and relationship to study vaccine. AEs through 49 days after first study vaccination; all MAAEs

through 35 days after first study vaccination; and MAAEs related to study vaccine; SAEs; or AESI through EOS will be listed separately and summarised by study vaccine group.

Vital sign measurements will be summarised by study vaccine group using descriptive statistics at baseline and following study vaccination.

Concomitant medications will be provided in a data listing with preferred drug name as coded using the World Health Organisation drug dictionary.

